3.2.2 Secondary Efficacy Analysis

Only for the Day 99 RVNA analysis base on PPS, the Day 99 RVNA results are treated as missing if the Day 99 RVNA blood sampling date was more than Day 110 away after the first dose of vaccine.

3.2.2.1 GMC of RVNA on Days 4, 15, 43, 99, 183, 365 Post-Dose

The primary analysis, subgroup analysis, and sensitivity analysis are performed using the same methods as that used for RVNA on Day 8 post-dose. In addition, mean RVNA versus time profiles (linear and semi-logarithmic) and scatter plots of BMI versus RVNA at each scheduled visit post-baseline will be created with scheduled sampling time points.

3.2.2.2 Positive Rate of RVNA on Days 4, 8, 15, 43, 99, 183, and 365 Post-Dose

3.2.2.2.1 Primary Analysis

The positive rates of RVNA on Days 4, 8, 15, 43, 99, 183, and 365 post-dose will be described by the number and percentage of subjects, and the inter-group differences will be compared using a chi-square test or an exact probability test (expected value < 5 in either cell), and inter-group differences in positive rates and their 95% CIs will be calculated based on Wald or Clopper-Pearson.

In addition, rate differences and P-values adjusted for the stratification factor of study site will be calculated using the CMH. A bar graph of RVNA concentrations will be created by scheduled visits.

3.2.2.2.2 Subgroup Analysis

Same as those in Section 3.2.1.1.2.

3.2.2.2.3 Sensitivity Analysis

Based on the PPS only, a sensitivity analysis will be performed after excluding the deviations in post-dose RVNA from geometric mean concentration \pm 3 times the geometric SD using the same method as the primary analysis.

3.2.2.3 AUEC₁₋₁₅ of RVNA GMC post-dose

The AUEC₁₋₁₅ of RVNA GMC will be calculated using the trapezoidal method. The primary analysis, subgroup analysis, and sensitivity analysis will be performed using the same method as that used for RVNA on Day 8 post-dose.

3.3 Safety Analysis

Based on the actual SS, the safety analysis will be performed by different treatment groups.

3.3.1 Drug Exposure

Based on the actual SS and PPS, the treatment compliance of lyophilized rabies vaccine for human use will be descriptively by treatment groups. The treatment compliance is equal to the actual number of doses divided by the planned number of doses multiplied by 100%, with the result rounded to one decimal place.

For “whether the investigational products were injected” and “whether there were any vaccination abnormalities”, these 2 questions will be summarized descriptively by the number and percentage of subjects who receive investigational products (including SYN023 and HRIG) and lyophilized rabies vaccine for human use. In addition, the number of doses and duration of exposure of lyophilized rabies vaccine for human use will be summarized by treatment groups.

The duration of exposure (days) is equal to last dose date minus first dose date plus 1. The duration of exposure includes the in-between period of discontinuation.

In addition, the administration information of the investigational product will be tabulated, mainly including: date of administration, time of administration, route of injection, injected wound site, occurrence of injection abnormalities, etc.

3.3.2 Adverse Events

Adverse events (AEs) will be coded using MedDRA 23.1 or the latest version of the dictionary prior to database lock. A treatment-emergent adverse event (TEAE) is defined as an adverse event that occurs on or after the injection date of investigational product and within 43 days after the investigational product injection, or an adverse event that worsens during the treatment compared with the condition prior to treatment, or an SAE that occurs 43 days after investigational product injection. If the start date of an AE is incomplete, it will be handled according to Section 2.3.4.2 Handling Rules of Missing Data.

The solicited AEs occurring within 7 days after injection include AEs at injection site (local) and non-injection site (systemic), among which, injection site (local) AEs include: injection site pain, pruritus, swelling, induration, redness, and rash. AEs at non-injection site (systemic) include: pyrexia, headache, rash, pruritus, urticaria, dyspnea, cough, chills, chest pain, arthralgia, myalgia.

The investigator should assess the severity of adverse events with reference to the Toxicity Grading Scale for Healthy Adult and Adolescent Volunteers Enrolled in Preventive Vaccine Clinical Trials 2007 and in combination with clinical practice (hereinafter referred to as Severity Criteria 1), see Solicited Adverse Events and Other Adverse Events in CRF for details; In addition, further assessment of severity will be performed based on Appendix 1 (hereinafter referred to as Severity Criteria 2) for pyrexia, injection site swelling, redness, induration only, and rash under solicited adverse events.

The number and percentage of subjects with at least 1 TEAEs and number of episodes of TEAEs will be summarized as follows:

- Any TEAEs
 - TEAEs within 30 minutes after investigational product injection
 - TEAEs within 7 days after investigational product injection
 - TEAEs within 8-43 days after investigational product injection
 - TEAEs unrelated to investigational product
 - TEAEs related to investigational product
 - TEAEs with Grade 3 or above in severity (Severity Criteria 1/2)
 - SAEs
 - TEAEs with Grade 3 or above in severity (Severity Criteria 1/2)
 - SAEs

- TEAEs leading to withdrawal
- TEAEs leading to death
- Solicited TEAEs
 - TEAEs within 30 minutes after investigational product injection
 - TEAEs with Grade 3 or above in severity (Severity Criteria 1/2)
 - SAEs
 - TEAEs leading to withdrawal
 - TEAEs related to investigational product
 - TEAEs with Grade 3 or above in severity (Severity Criteria 1/2)
 - SAEs
 - TEAEs unrelated to investigational product
 - Solicited local TEAEs
 - TEAEs within 30 minutes after investigational product injection
 - TEAEs related to investigational product
 - TEAEs with Grade 3 or above in severity (Severity Criteria 1/2)
 - SAEs
 - TEAEs unrelated to investigational product
 - TEAEs with Grade 3 or above in severity (Severity Criteria 1/2)
 - Solicited local TEAEs
 - TEAEs within 30 minutes after investigational product injection
 - TEAEs related to investigational product
 - TEAEs with Grade 3 or above in severity (Severity Criteria 1/2)
 - SAEs
 - TEAEs unrelated to investigational product

- TEAEs with Grade 3 or above in severity (Severity Criteria 1/2)
- TEAEs at the injected wound site
- TEAEs within 30 minutes after investigational product injection
- TEAEs related to investigational product
- TEAEs with Grade 3 or above in severity (Severity Criteria 1/2)
- SAEs
- TEAEs unrelated to investigational product
- TEAEs with Grade 3 or above in severity (Severity Criteria 1/2)
- TEAEs at injection site other than the wound site(s)
- TEAEs within 30 minutes after investigational product injection
- TEAEs related to investigational product
- TEAEs with Grade 3 or above in severity (Severity Criteria 1/2)
- SAEs
- TEAEs unrelated to investigational product
- TEAEs with Grade 3 or above in severity (Severity Criteria 1/2)
- Unsolicited TEAEs
- TEAEs within 30 minutes after investigational product injection
- TEAEs within 7 days after investigational product injection
- TEAEs within 8-43 days after investigational product injection
- TEAEs related to investigational product
- TEAEs with Grade 3 or above in severity (Severity Criteria 1)
- SAEs
- TEAEs unrelated to investigational product

- TEAEs with Grade 3 or above in severity (Severity Criteria 1)
- SAEs
- TEAEs leading to withdrawal

The number and percentage of subjects with TEAEs and number of episodes of TEAEs will be summarized by SOC and PT, respectively, as follows:

- Any TEAEs
- Unsolicited TEAEs
- TEAEs with Grade 3 or above in severity (Severity Criteria 1)
- TEAEs related to investigational product
- TEAEs related to investigational product and with Grade 3 or above in severity (Severity Criteria 1)
- TEAEs leading to withdrawal
- Unsolicited TEAEs with Grade 3 or above in severity (Severity Criteria 1)
- Unsolicited TEAEs Related to Investigational Product
- Unsolicited TEAEs related to investigational product and with Grade 3 or above in severity (Severity Criteria 1)
- SAEs
- SAEs related to investigational product
- Unsolicited TEAEs Leading to Withdrawal

In addition, the number and percentage of subjects with TEAEs will be summarized by the maximum severity reported (severity criteria 1/severity criteria 2), SOC, and PT; and the number and percentage of subjects with TEAEs will also be summarized by the reported causal relationship with investigational products (definitely related > probably related > possibly related > unlikely related > unrelated), SOC and PT. If the causal relationship with investigational products is missing, it should be imputed as “possibly related”. The details are as follows:

- Summary of unsolicited TEAEs by causal relationship with investigational product, SOC, and PT
- Summary of TEAEs by causal relationship with investigational product, SOC, and PT
- Summary of unsolicited SAEs by causal relationship with investigational product, SOC, and PT

- Summary of SAEs by causal relationship with investigational product, SOC, and PT
- Summary of unsolicited TEAEs with Grade 3 or above in severity by causal relationship with the investigational product, SOC, and PT
- Summary of TEAEs with Grade 3 or above in severity by causal relationship with the investigational product, SOC, and PT
- Summary of unsolicited TEAEs by maximum severity, SOC, PT (Severity Criteria 1)
- Summary of TEAEs by maximum severity, SOC, PT (Severity Criteria 1)
- Summary of unsolicited TEAEs related to investigational product by maximum intensity, SOC, and PT (Severity Criteria 1)
- Summary of TEAEs related to investigational product by maximum intensity, SOC, and PT (Severity Criteria 1)

In addition, the number and percentage of subjects with solicited TEAEs and number of episodes of such TEAEs will be summarized by symptom as follows:

- Summary of solicited TEAEs by symptom
- Summary of solicited TEAEs related to investigational product by symptom
- Summary of solicited TEAEs unrelated to investigational product by symptom
- Summary of solicited TEAEs by symptom and severity (Severity Criteria 1/2)

The number of AEs will be calculated with the actually occurred total number of episodes of the AE when calculating the TEAEs of a subject who has more than one episode of one TEAE (as determined by PT). Similarly, when calculating the TEAEs of a subject who has more than one TEAEs in a SOC, the number of AEs will also be calculated with the actually occurred number of episodes if the AE in that system organ class. Causal relationship with investigational products will be classified as “related” and “unrelated” when calculating the AEs. The “related” includes “definitely related”, “probably related”, and “possibly related”; and “unrelated” includes “unlikely related” and “unrelated”.

In summary of each type of TEAEs, TEAEs will be displayed by SOCs in descending order of the total numbers of subjects in all SOCs. In case there are equal number of subjects in certain SOCs, TEAEs will be displayed by SOCs in alphabet order of initials of the SOCs; in case there are equal number of subjects in one SOC, TEAEs will be displayed by PT in descending order of the total number

of subjects in all PTs; and in case there are equal number of subjects in certain PTs, TEAEs will be displayed in alphabet order of initials of the PTs.

All AEs will be displayed in listing, including the AE term, start date, end date, occurring within 30 minutes or not, maximum severity, serious adverse event or not, SAE classification, causal relationship with the investigational product. At the same time, solicited adverse events, AEs leading to withdrawal, SAEs, and AEs leading to death will be displayed in separate listings.

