7.3 Safety Endpoints

- All AEs regardless of related or un-related with IMPs within 30 minutes post administration will be collected ;
- Injection/vaccination sites (local)'s AE and (Systemic) adverse events occurring at sites other than the injection/vaccination sites within 1~8 days post administration;
- All AEs related or unrelated to the study drug occurring within 1~43 days post administration;
- Grade 3 or higher AEs occurring within 1~43 days post administration;
- All SAEs related or unrelated to the study drug occurring during the study;
- Pregnancy events occurring within 6 months after administration (pregnancy status and outcome);
- AEs/SAEs leading to withdrawal.

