13.5.4.1 AEs

The system organ classification and preferred term classification of AE will be coded by the current edition of MedDRA. Analysis of AE will be based on treatment-emergent AE (TEAE), i.e., an undesirable event not present prior to medical treatment, or an already present event that worsens during the treatment. The number of TEAE subjects and TEAE cases, and TEAE incidence will be summarized by treatment group, system organ class and preferred term:

Any TEAE that occur within 43 days post administration, n TEAE of Grade 3 or above, TEAE related to the study drug, TEAE leading to subject's suspension of treatment, and TEAE leading to subject's withdrawal from the test; solicited local adverse response, solicited systemic adverse response, SAE, and SAE related to the IMPs.

In addition, the severity of TEAE occurring within 43 days after injection and its correlation with the study drug will also be summarized by treatment group, system organ class and preferred term. For each subject, only the most severe or the most relevant term is recorded.

List of SAE by treatment group and list of TEAE leading to withdrawal within 43 days after administration are provided.

Solicited systemic events (Fever, headache, rash, itching, urticaria, dyspnea, cough, chills, chest pain, joint pain, myalgia) that occur within 8 days post administration in each group will be described and analyzed according to symptoms. Solicited systemic events that lead to the

suspension of study are analyzed in the same manner.

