1.2.3 Safety endpoints

- All, related, and unrelated AEs within 30 minutes post-dose;
- AEs of injection site (local) and non-injection site (systemic) on Study Days 1~8;
- All, related, and unrelated AEs on Study Days 1~43;
- All, related, and unrelated AEs with Grade 3 or above in severity on Days 1~43;
- All, related, and unrelated SAEs during the study;
- Pregnancy events (pregnancy status and outcomes) occurring within 6 months;
- AE/SAEs leading to withdrawal.

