1.3 Study Design

1.3.1 Overall Design

This is a randomized, double-blind, positive-controlled clinical study. A total of 1,000 subjects aged 18 years and older with Category III rabies exposures are planned to be enrolled and will be randomized at a 3:1 ratio into the study group and the control group. The subjects in both groups will be immunized with rabies vaccine according to the post-exposure prophylaxis (PEP) procedure of rabies. The sample size and assignment of rabies prophylaxis for both groups are shown in the following table:

Group	Sample Size	Investigational Product	Dosage and Administration	Injection Time
Study group	750	SYN023	0.3 mg/kg, infiltration injection at the wound *	Day 1
		Rabies vaccine for human use	0.5 mL, intramuscular injection into the deltoid muscle of the upper arm	Days 1, 4, 8, 15, and 29 (Essen regimen)

Control group	250	HRIG	20 IU/kg, infiltration injection at the wound *	Day 1
		Rabies vaccine for human use	0.5 mL, intramuscular injection into the deltoid muscle of the upper arm	Days 1, 4, 8, 15, and 29 (Essen regimen)

* In case there are remaining amounts of Drug after infiltration injections at all wounds, the remaining Drug should be injected into muscles remote from the Drug injection site (the dorsal muscle group ipsilateral to the wound for areas above the waist, and the mid-lateral thigh muscle group ipsilateral to the wound for areas below the waist)

At enrollment (Day 1), an infiltration injection of SYN023 or HRIG should be performed at the wound, meanwhile, 1 dose of lyophilized rabies vaccine for human use (Vero cells) should also be injected intramuscularly into the deltoid muscle of the upper arm. According to the Essen regimen, one dose of lyophilized rabies vaccine for human use (Vero cells) will also be injected on Study Days 4, 8, 15, and 29 respectively. A total of 8 venous blood samples at a volume of approximately 3.0 mL each will be collected from all subjects prior to dose and on Study Days 4, 8, 15, 43, 99, 183, 365 post-dose, and will be used for the evaluation of efficacy endpoints. In addition, the subjects will be followed up for incidence of rabies and survivability. All blood samples will be tested for RVNA using a rapid fluorescence focus inhibition test. In addition, solicited AEs occurred within Days 1-8 post-dose, all other AEs occurred within Days 1-43 post-dose, as well as pregnancies up to 6 months post-dose and all SAEs throughout the study will be collected.

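### SAEs after Day 43 count as TEAEs in the SAP, so the Grade 3 or above tables, and to a lesser extent the any-TEAE and related/unrelated tables, do not report the Day 1-43 endpoints

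*SAP*

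**What the plan says.** **Endpoints.** SAP 1.2.3 lists "All, related, and unrelated AEs on Study Days 1~43" and "All, related, and unrelated AEs with Grade 3 or above in severity on Days 1~43". SAEs are a separate endpoint with a longer window: "All, related, and unrelated SAEs during the study". Protocol 7.3 gives the same limit for severity: "Grade 3 or higher AEs occurring within 1~43 days post administration".

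**Collection.** SAP 1.3.1 collects "all other AEs occurred within Days 1-43 post-dose", and SAEs throughout the study. Protocol 8.1.4 agrees.

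**TEAE definition.** SAP 3.3.2 counts as a TEAE an event occurring "on or after the injection date of investigational product and within 43 days after the investigational product injection", or one that worsens on treatment, "or an SAE that occurs 43 days after investigational product injection".

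**Tables.** In the SAP 3.3.2 overview, the only time-limited rows are those for 30 minutes, 7 days and 8-43 days. As printed, the related, unrelated and Grade 3 or above rows stand beside these rows and are not crossed with them. The SOC/PT, maximum-severity and causality tables state no window.

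**Protocol analysis text.** Protocol 13.5.4.1 opens its list with "Any TEAE that occur within 43 days post administration". Its next paragraph limits the summary of severity and relatedness by SOC and PT to TEAEs within 43 days of injection. SAP section 5 lists only the Wald and CMH additions as changes from the protocol.

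**The concern.** A table of Grade 3 or above TEAEs will be read as the Day 1-43 endpoint. Under the SAP definition it contains every Grade 3 or above AE up to Day 43, followed by serious events only, up to the data cut. A non-serious Grade 3 event on Day 60 cannot enter, whereas a Grade 3 hospitalisation of any cause on Day 200 does. The figure is then neither a 43-day rate nor a one-year rate.

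Two reports are planned, one after Day 99 and one after a year. An endpoint whose window closed at Day 43 could therefore appear with two different values in two submissions. The protocol's 43-day limit on the severity and relatedness summary would also have been dropped without being declared.

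**Working it through.** The plan states no figure for this point, so there is none to reproduce. The check compares the texts, counts days and then illustrates the size.

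**1. What the last part of the definition adds.** SAEs up to Day 43 already qualify under the first part. The SAE clause can therefore only add later ones; on any other reading it is redundant.

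**2. Endpoint against planned table.**

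| Quantity | Endpoint window (SAP 1.2.3) | Planned table (SAP 3.3.2) |
|---|---|---|
| Any AE | Days 1-43 | Any TEAEs, no overall limit; rows for 7 days and 8-43 days |
| Grade 3 or above | Days 1-43 | No window |
| Related / unrelated | Days 1-43 | No window |
| SAEs | Whole study | Listed among the TEAE summaries; reach past Day 43 only through the SAE clause |

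Solicited events are confined to about the first week, so the solicited tables are essentially unaffected. The related tables gain only late SAEs that are judged related, or whose causality is missing and is imputed as possibly related (SAP 3.3.2).

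**3. Length of the SAE-only period.**
- By Day 365: 365 - 43 = 322 days; 322/365 = 88% of the study; 322/43 = 7.5 times the endpoint window.
- By Day 99: 99 - 43 = 56 days; 56/43 = 1.3 times the endpoint window.

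**4. Inflation of the Grade 3 or above rate.** Neither document gives an SAE or Grade 3 rate for this population, so these inputs are assumptions: late SAEs at λ = 1-5% per year, all Grade 3 or above and independent of early events; Day 1-43 incidence p = 1-5%.

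Late risk: q = 1 - exp(-λ × (end - 43)/365). Table rate: 1 - (1 - p)(1 - q).

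With p = 3% and λ = 3%:
- Day 99: q = 0.0046; table rate 1 - 0.97 × 0.9954 = 0.0345.
- Day 365: q = 0.0261; table rate 1 - 0.97 × 0.9739 = 0.0553.

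| Arm | Endpoint | Table at Day 99 | Table at Day 365 |
|---|---|---|---|
| SYN023 (750) | 22.5 | 25.8 | 41.5 |
| HRIG (250) | 7.5 | 8.6 | 13.8 |

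Over the whole grid, the table exceeds the endpoint by a factor of 1.03-1.76 at Day 99 and 1.17-5.27 at Day 365.

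**5. Effect on the comparison.** Assume true Day 1-43 rates of 4% (SYN023) and 2% (HRIG): ratio 2.0, difference 2.0 points. Add the same late risk q to both arms.

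| q | SYN023 | HRIG | Ratio | Difference (points) |
|---|---|---|---|---|
| 2% | 5.92% | 3.96% | 1.49 | 1.96 |
| 4% | 7.84% | 5.92% | 1.32 | 1.92 |
| 6% | 9.76% | 7.88% | 1.24 | 1.88 |

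**6. A rough anchor from the documents.** Protocol 6.3.1 to 6.3.4 report one SAE in 15 + 30 + 164 + 33 = 242 subjects. Follow-up was 15×84 + 30×84 + 164×112 + 33×85 = 24,953 days, or 68.4 person-years, if everyone completed. The rate is 1/68.4, about 1.5% per year. At 1.5%:
- Day 99: q = 0.23%; 4.2% against 2.2%; ratio 1.90.
- Day 365: q = 1.3%; 5.3% against 3.3%; ratio 1.60.

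This rests on one event, in trials described as in healthy subjects. The exact Poisson 95% limits for one event are 0.025 and 5.57, or 0.04% to 8.1% per year. The anchor does not narrow the assumed range.

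**The case against.** **The tables are descriptive.** SAP 3.3.2 plans counts and percentages, with no test between arms, and both arms share the definition. This stands. A reader might infer that a safety signal would be hidden or the comparison biased. The documents do not support that: only the ratio shrinks, and the absolute difference stays within 0.12 points of the true 2.0 in step 5.

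**The data are not lost.** The 7-day and 8-43-day rows come close to giving the any-TEAE count for the endpoint window, although a subject may be in both. The AE listings carry start date, severity, seriousness and causality. This also stands, but it shows that the endpoint tables could be derived, not that they are planned. List indentation is partly lost in the text available, so the statement that no row is crossed with the window rests on the list as printed.

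**The protocol does not limit every TEAE item to 43 days.** This is correct. The protocol's TEAE definition has no day limit, and in its list the 43 days attach to the first item; the Grade 3, related, withdrawal and SAE items follow without a limit of their own. A reader might take the limit to cover all of them, but the text does not settle that. The undeclared departure rests on the next paragraph, which does limit the severity and relatedness summary, and on the endpoint in protocol 7.3.

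**Deleting the SAE clause would do harm.** This stands against the obvious repair. The SAE, death and withdrawal summaries sit among the TEAE tables, so deletion alone could cut them at Day 43 and miss the whole-study SAE endpoint.

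**The illustrated sizes may be high.** Not every SAE is Grade 3 or above, since hospitalisation alone makes an event serious, and the anchor of 1.5% per year is below the 2-6% late risks in step 5. Both are fair reasons to treat the sizes as illustrative.

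**Conclusion.** The point holds. Followed as written, the SAP gives overall and unsolicited Grade 3 or above tables that do not report the endpoint in SAP 1.2.3 and protocol 7.3. They also depart, undeclared, from the 43-day severity and relatedness summary in protocol 13.5.4.1. The any-TEAE and related/unrelated tables are affected to a lesser extent. The related tables are touched only by late SAEs judged related or with imputed causality, so it would be wrong to infer that they are distorted as much as the Grade 3 tables.

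Rates are inflated and the ratio is diluted, while the absolute difference is nearly unchanged. How far depends on late-SAE rates that the documents do not give for this population, and on the assumption that every late SAE is Grade 3 or above. That the windows do not match depends on neither. This is a mismatch between endpoint and table in descriptive safety reporting, and no efficacy conclusion depends on it. It should be corrected because the same endpoint would otherwise be able to take two values in two submissions.

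**What to change.** 1. In SAP 3.3.2, restrict the any-TEAE, unsolicited, Grade 3 or above, related/unrelated, SOC/PT, maximum-severity and causality TEAE tables to onset on Study Days 1-43. State the limit in study days: under SAP 2.3.2 the injection date is Day 1, so an event 43 days after injection falls on Study Day 44.
2. In the same revision, define the SAE, related-SAE, death and AE/SAE-withdrawal tables as whole-study and independent of the TEAE window, so that they are not cut at Day 43. Once that is done, the late-SAE clause can be removed. Alternatively, keep the clause and add the Day 1-43 filter to the tables in item 1.
3. List the change in SAP section 5.

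The cost is SAP wording and a date filter in the table programs. No additional data are needed.

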Study Suspension or Termination	
 Based on any new information of the IMP obtained from this study or other studies that the Sponsor, the Investigator, the IRB, and the National Drug Regulatory Authority (NMPA) determine to suspend the trial with the analysis of subject risk/benefit evaluation. When any subject dies or experiences any serious life-threatening adverse reaction related to the study drug during the study; When the number of subjects with Grade 3 or higher RELATED systemic adverse reactions accounts for 20% or more of the number of subjects receiving the study product during the trial. 
In case of the above circumstances for suspension, the trial needs to be

	
suspended, and shall be reported to the Institutional Review Board for the decision of continuity. If necessary, terminate the trial as the decision.
 
If the study is terminated earlier or suspended, the (DSMB will recommend to the sponsor termination of the protocol and) Sponsor will notify the investigators, the Institutional Review Board, and the drug authorities of the reason for the suspension or termination immediately in accordance with relevant regulations.
 
Regardless of the reason for the early termination of the study, the investigators should notify all subjects immediately of such termination and carry out appropriate follow-up visits on the conditions of the subjects.

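### The SAP adverse-event overview lists the solicited local block twice and has no solicited systemic block, so subjects with any solicited systemic event are not counted

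*SAP*

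**What the plan says.** The overview in SAP 3.3.2 gives the number and percentage of subjects with at least one event, and the number of episodes, for a series of categories. After the pooled solicited block comes a block headed "Solicited local TEAEs", then a second block with the same heading. Blocks for the injected wound site and for other injection sites follow, and then the unsolicited events. No block is headed solicited systemic.

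Four other places bear on what was intended:

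- SAP 1.2.3 lists as a safety endpoint "AEs of injection site (local) and non-injection site (systemic) on Study Days 1~8". Protocol 7.3 likewise names a local and a systemic component.
- The text of SAP 3.3.2 that precedes the overview divides solicited events into local and systemic, and defines the second group: "AEs at non-injection site (systemic) include: pyrexia, headache, rash, pruritus, urticaria, dyspnea, cough, chills, chest pain, arthralgia, myalgia".
- Protocol 13.5.4.1 includes among the planned summaries "solicited local adverse response, solicited systemic adverse response, SAE, and SAE related to the IMPs".
- SAP section 5, on changes from the protocol's analysis plan, mentions only the Wald and CMH additions. It does not say that the systemic summary was dropped.

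**The concern.** Programmed as written, the overview would print the solicited local block twice and would contain no solicited systemic block. The report could then state what share of SYN023 and HRIG recipients had any solicited local reaction, but not the matching share for systemic reactions. That share is the natural headline figure for the systemic half of a named endpoint in a comparative safety evaluation. The question is whether the SAP's other adverse-event outputs supply it.

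**Working it through.** No sample size, power or error rate is involved, and the plan gives no figure to reproduce. The check compares the overview with what the documents require, and then asks whether the missing count follows from the other planned tables.

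**Step 1. Count the blocks in the SAP 3.3.2 overview.**

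| Heading | Times listed | Sub-rows, in order |
|---|---|---|
| Solicited local | 2 | 30 minutes; related; Grade 3 or above; SAE; unrelated; Grade 3 or above |
| Solicited systemic | 0 | none |

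The six sub-rows agree line for line between the two local blocks, so the second adds nothing to the first.

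**Step 2. Compare with the requirement.** SAP 1.2.3, Protocol 7.3 and Protocol 13.5.4.1 each name a systemic component beside the local one. The overview has only the local one.

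**Step 3. Try to recover the count from the by-symptom tables.** SAP 3.3.2 plans four: all solicited events, related, unrelated, and by severity. Each gives subjects per symptom. If symptom *i* occurs in a proportion *p_i* of an arm, the proportion with any of the 11 symptoms satisfies only

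max(*p_i*) ≤ *p_any* ≤ min(1, Σ*p_i*).

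The lower limit is reached when the same subjects have every symptom, and the upper limit when no subject has two. The documents give no expected symptom rates for this trial, so the rates below are assumptions:

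| Assumed rate per symptom | Lower limit | Upper limit (11 × rate) |
|---|---|---|
| 1% | 1% | 11% |
| 2% | 2% | 22% |
| 5% | 5% | 55% |

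At 2%, that is 15 to 165 of the 750 planned SYN023 subjects (0.02 × 750 and 0.22 × 750) and 5 to 55 of the 250 planned HRIG subjects (0.02 × 250 and 0.22 × 250).

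**Step 4. Try subtraction within the overview.** With *N* for numbers of subjects,

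*N*(systemic) = *N*(any solicited) − *N*(local) + *N*(local and systemic).

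The overview gives the first two terms on the right but not the third. So *N*(systemic) is known only to lie between *N*(any solicited) − *N*(local) and *N*(any solicited). Episode counts can be subtracted; subject counts cannot.

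**Step 5. Try the remaining outputs.** The SOC and PT tables of all events mix solicited with unsolicited events and give no pooled systemic row. No by-symptom table crosses relatedness with severity, so related Grade 3 or above solicited systemic events have no summary of their own. The listing of solicited events holds the subject-level information, but counting from it amounts to making the missing table.

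**Step 6. Check that the by-symptom tables are unambiguous.** SAP 3.3.2 puts rash and pruritus on both the local list (6 terms) and the systemic list (11 terms). The tables are not stated to be split by site. If they are not split, a row for rash or pruritus could combine the two, and even the limits in Step 3 could not be formed cleanly.

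**The case against.** The strongest reply is that this is a label error in one table and that the systemic events are well covered elsewhere. Protocol 13.5.4.1 itself says that the solicited systemic events are to be described by symptom, and SAP 3.3.2 does that with subject numbers, percentages and episodes. All events, related events and related Grade 3 or above events are also tabulated by SOC and PT, and solicited events have their own listing. The pooled solicited block has its own 30-minute, related, Grade 3 or above and SAE rows. Two identical blocks make no sense as a plan, so a programmer would probably notice, and the table shells are not among the documents.

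Most of this stands, and it limits the point. A reader might infer that the systemic half of the endpoint is not summarised at all, or is absent for all 1,000 subjects. The documents do not support that: each of the 11 symptoms is to be reported by arm. Only the pooled count and its breakdowns are missing.

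A reader might also link the gap to the suspension rule, which the protocol synopsis words in terms of "Grade 3 or higher RELATED systemic adverse reactions" at a 20% threshold. That does not hold either. The rule applies while the trial is running, whereas the SAP analyses follow the Day 99 database lock and unblinding (Protocol 8.2.5, SAP section 4). The rule is not limited to solicited events, so a corrected block would not give the rate it uses.

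What the reply does not remove is that the text, as it stands, omits a summary that Protocol 13.5.4.1 names, and that no other planned table yields it.

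**Conclusion.** The point holds at minor severity. The overview repeats the solicited local block and lacks the solicited systemic one. As a result, the subject-level count of any solicited systemic event, with its 30-minute, related, unrelated, Grade 3 or above and SAE rows, is not planned and can only be bounded from the other tables. The size is one pooled block of one overview table. No efficacy estimate, hypothesis, error rate or endpoint definition changes.

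Two judgements are involved. The first is that the duplicate is a slip and not a decision, which fits the endpoint wording and the absence of any declared removal in SAP section 5. The second is that the first of the two blocks is the mislabelled one, because the wound-site and other-injection-site blocks, which subdivide local events, follow the second. The text does not settle this, and list indentation is lost in the available copy. Relabelling either block would restore the analysis.

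**What to change.** In SAP 3.3.2, rename one of the two duplicate blocks *Solicited systemic TEAEs* and keep the same sub-rows. The first is the better choice, so that the wound-site and other-injection-site blocks stay beneath the local one. Use the same heading in the table shells. Also state that the by-symptom tables are presented separately for local and systemic events, so that rash and pruritus are not merged across sites.

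The cost is one word in the overview, one sentence on the by-symptom tables, and the matching shell edits. No new data are needed, because SAP 3.3.2 already classes solicited events as local or systemic.
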